### **16.3.2. Secondary Endpoint**

#### **Progression Free Survival 2 (PFS2)**

PFS is defined as the time from randomization to the second objective disease progression, or death from any cause, whichever occurs first. Patients alive and for whom a second objective disease progression has not been observed should be censored at the last time known to be alive and without second objective disease progression. In situations where OS and PFS2 cannot reliably be determined, it may be possible to rule out significant lack of efficacy of further treatments by looking at the outcome of the next line therapy. For this analysis, an event is defined as second objective disease progression, or death from any cause, or the start of the CLL therapy after next line treatment, whichever occurred first (EMA guideline 13 DEC 2012). Various schemes will be assessed for missing data imputation if needed.

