## 2. SYNOPSIS

Name of Sponsor/Company: Celgene Corporation	
Name of Investigational Product: lenalidomide	
Protocol Number: CC-5013-CLL-002	
Protocol Title: A PHASE 3, MULTICENTER, RANDOMIZED, DOUBLE-BLIND, PLACEBO-CONTROLLED, PARALLEL-GROUP STUDY OF THE EFFICACY AND SAFETY OF LENALIDOMIDE (REVLIMID®) AS MAINTENANCE THERAPY FOR PATIENTS WITH B-CELL CHRONIC LYMPHOCYTIC LEUKEMIA FOLLOWING SECOND-LINE THERAPY	
Indication: Maintenance therapy in subjects with relapsed or refractory B-cell chronic lymphocytic leukemia (CLL) who have achieved at least partial response (PR) to second-line therapy.	

Study Duration: Subjects randomized to the lenalidomide treatment arm and on treatment at the time of Amendment #10 may, at the discretion of the investigator, continue on lenalidomide study treatment until disease progression (PD) develops. Subjects randomized to the placebo treatment arm and on treatment at the time of Amendment #10 will enter the survival follow-up period. Subjects who discontinue study treatment prematurely for reasons other than PD and subjects who develop PD (including disease transformation) will enter the survival follow-up period.
 
Subjects will be followed until all subjects in the study have been followed for at least 5 years from the last randomization, October 2020, (or have died/become lost to follow-up before the 5 years).
 
Amendment #11:
 
Subjects currently on lenalidomide treatment will discontinue lenalidomide treatment immediately and complete the Treatment Discontinuation assessment. The subjects will then transition to the survival follow-up period.
	
Phase of development: Phase 3

Objectives:
 
Primary:
 
 
To compare the efficacy of lenalidomide versus placebo maintenance therapy.
 
 
Secondary:
 
 
To evaluate the safety of lenalidomide versus placebo maintenance therapy.
 
	

Study Endpoints:
 
Primary
 
 
Overall Survival (OS)
 
	

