#### Amendment #11:

Subjects currently on lenalidomide treatment will discontinue lenalidomide treatment immediately and complete the Treatment Discontinuation assessment. The subjects will then transition to the survival follow-up period.

Eligible subjects must have been treated with a purine analog-, a bendamustine-, an anti-CD20 antibody-, or a chlorambucil-based regimen in first and/or second line and must have achieved at least PR to second-line induction therapy of sufficient duration. Alemtuzumab- containing regimens will also be allowed for those patients with 17p deletion. Subjects who achieve stable disease (SD) only or who develop progressive disease (PD) at any time during induction therapy will not be eligible for participation in this study.

Approximately, three hundred twenty (320) subjects with PR, nPR, CRi, CR or MRD-negative CR will be enrolled and randomized (1:1) into two arms: placebo daily or lenalidomide 2.5 mg daily on days 1-28 of the first cycle. If the 2.5 mg dose level is well tolerated, escalation to 5 mg daily on days 1-28 of each 28-day cycle is permitted starting with the second cycle. If a subject develops a Grade 1 or 2 adverse event, the drug may be interrupted until resolution, however the subject must complete one full cycle at the 2.5 mg dose level prior to escalation to the 5 mg dose level. For those subjects who tolerate the 5 mg dose without unacceptable toxicity, escalation to 10 mg daily on days 1-28 of each 28-day cycle after 5 continuous cycles at 5 mg will be permitted. Each treatment arm will be stratified according to 1) the response to second-line induction therapy (PR, nPR, CRi or CR versus MRD-negative CR); 2) age ( $\leq 70$  versus  $> 70$  years); and 3) presence of at least one of the following poor prognostic factors: 11q deletion, 17p deletion, unmutated IgVH or  $\beta 2M > 4.0$  mg/L (Yes versus No versus Unknown).

The subjects randomized to the lenalidomide treatment will continue to receive lenalidomide up to PD. For those subjects who discontinue therapy for reasons other than PD (ie, unacceptable toxicity) they will transition to the survival follow-up period.

Subjects who discontinued from the study drug will be followed every 24 weeks for survival, subsequent CLL therapies, response to next therapy and progression following next therapy, and

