**After Study Discontinuation:**

Upon discontinuation of study drug, subjects will be followed every 24 weeks for survival, information on other CLL treatments, response to next therapy and progression following next therapy, and second primary malignancies (reported as SAEs). Subjects will be followed until all subjects in the study have been followed for at least 5 years from the last randomization, October 2020 (or have died/become lost to follow-up before 5 years).

FCBP with regular menstrual cycles discontinued from treatment must have a pregnancy test on day 28 after the treatment discontinuation visit. FCBP with irregular cycles discontinued from treatment must have a pregnancy test on days 14 and 28 after the treatment discontinuation visit.

SAEs will continue to be collected for the first 30 days after the treatment discontinuation visit. Following 30 days post the treatment discontinuation visit, only SAEs related to maintenance therapy will be collected for the study duration. Second primary malignancies must be reported as SAEs. This includes any second primary malignancy, regardless of causal relationship to study medication, occurring at any time for the duration of the study, from the time of signing the informed consent up to and including progression free follow-up and survival follow-up.

[REDACTED]

[REDACTED]

[REDACTED]

[REDACTED]

[REDACTED]

[REDACTED]

[REDACTED]

[REDACTED]

[REDACTED]

[REDACTED]

[REDACTED]

[REDACTED]

[REDACTED]

[REDACTED]

[REDACTED]

[REDACTED]

[REDACTED]

[REDACTED]

[REDACTED]

[REDACTED]

[REDACTED]

[REDACTED]

[REDACTED]

[REDACTED]

[REDACTED]

[REDACTED]

[REDACTED]

[REDACTED]

[REDACTED]

[REDACTED]

[REDACTED]

[REDACTED]

[REDACTED]

[REDACTED]

[REDACTED]

[REDACTED]

[REDACTED]

[REDACTED]

[REDACTED]

[REDACTED]

[REDACTED]

[REDACTED]

[REDACTED]

[REDACTED]

[REDACTED]

[REDACTED]

[REDACTED]

[REDACTED]

[REDACTED]

[REDACTED]

[REDACTED]

[REDACTED]

[REDACTED]

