11.2.4. Progression Free Survival 2 (PFS2)

PFS2 is defined as the time from randomization to second objective disease progression, or death from any cause, whichever occurred first. Patients alive and for whom a second objective disease

progression has not been observed should be censored at the last time known to be alive and without second objective disease progression. In situations where OS and PFS2 cannot reliably be determined, it may be possible to rule out significant lack of efficacy of further treatments by looking at the outcome of the next line therapy. For this analysis, an event is defined as second objective disease progression, or death from any cause, or the start of the CLL therapy after next line treatment, whichever occurred first [REDACTED]

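### PFS2 counts the second objective progression after randomization, so progression on next-line therapy is not an event when it occurs if no earlier progression was documented

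*Protocol*

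**What the plan says.** Protocol 16.3.2 gives the definition under the heading for PFS2, although the sentence itself is labelled PFS: "PFS is defined as the time from randomization to the second objective disease progression, or death from any cause, whichever occurs first". SAP 11.2.4 has the same rule with the right label: "PFS2 is defined as the time from randomization to second objective disease progression, or death from any cause, whichever occurred first". In both, a living subject without a second progression "should be censored at the last time known to be alive and without second objective disease progression".

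Both also describe a fallback. It is introduced by "In situations where OS and PFS2 cannot reliably be determined", is worded as a possibility, and adds one event type: "or the start of the CLL therapy after next line treatment, whichever occurred first". It still counts the second objective progression.

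Several routes lead out of maintenance without progression.
- Protocol 8.1: "For those subjects who discontinue therapy for reasons other than PD (ie, unacceptable toxicity) they will transition to the survival follow-up period".
- Protocol synopsis, Study Duration: "Subjects randomized to the placebo treatment arm and on treatment at the time of Amendment #10 will enter the survival follow-up period".
- Amendment #11 stops lenalidomide at once for everyone still taking it and moves them to survival follow-up.

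In that period subjects are "followed every 24 weeks for survival, information on other CLL treatments, response to next therapy and progression following next therapy", and for second primary malignancies (Protocol 8.1, After Study Discontinuation). Protocol Table 2 schedules a response assessment every 28 days on treatment and at treatment discontinuation, but none in survival follow-up.

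Other passages point the other way. SAP 5.1 has early discontinuers followed until progression, and asks for the date and documentation of progression, if possible, from subjects who enter survival follow-up before it. Several creatinine rows of Protocol Table 6 also call for follow-up for PD after permanent discontinuation.

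**The concern.** PFS2 is the only secondary efficacy endpoint visible in the current protocol, and Protocol 16.3.3 names it among the endpoints compared by stratified log-rank test. Its purpose is to show how patients fare through the next line of treatment. A rule that counts progressions from randomization does this only if the first progression was recorded before next-line therapy began. Where it was not, failure of the next line is progression number one, and the clock keeps running.

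The current protocol creates such subjects by design, through stops without PD and through Amendments #10 and #11. The SAP recognises the situation for PFS: its Table 2 has a row for new anticancer treatment started with no claim of progression. PFS2 has no matching rule. If the arms contribute such subjects in different proportions, the PFS2 curves can separate or converge for reasons unrelated to treatment.

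**Working it through.** The documents give no PFS2 sample size, event count, power or alpha, so there is no planned figure to reproduce. The check has two parts.

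**Classifying the pathway.** Take a subject who stops without PD, starts next-line therapy with no progression documented, and then progresses on it.

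| Rule | Event at that progression? | When the subject becomes an event |
|---|---|---|
| PFS2 as written (Protocol 16.3.2, SAP 11.2.4) | No, it is the first progression | A further progression or death |
| Fallback (same sections) | No | A further progression, start of the CLL therapy after next-line treatment, or death |
| Progression after start of next-line therapy, or death | Yes | At that progression |

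**Illustrating the size.** Both arms were given identical true processes, so the true hazard ratio is 1.0.

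From the documents:
- 160 subjects per arm.
- A median of 20 months to leaving maintenance (the placebo PFS median in SAP 6.1, applied to both arms).

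Assumed:
- Median 15 months from there to progression on next-line therapy.
- Median 3 further months to the following therapy.
- Median survival 72 months.
- Follow-up uniform over 60 to 96 months.
- The share reaching next-line therapy without a documented first progression.

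Each setting used 60 replicates and a Cox model.

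| Share, lenalidomide / placebo | HR as written (mean events) | HR, fallback | HR, next-line rule | Next-line progressions not counted when they occurred (of 320) |
|---|---|---|---|---|
| 0% / 0% | 1.00 (289.6) | 1.00 | 1.00 | 0 |
| 10% / 10% | 1.02 (278.1) | 1.00 | 1.00 | 17.6 |
| 20% / 10% | 0.92 (272.4) | 0.99 | 1.00 | 26.6 |
| 30% / 10% | 0.83 (266.6) | 0.98 | 1.00 | 35.4 |
| 40% / 20% | 0.83 (254.3) | 0.98 | 1.00 | 54.0 |
| 10% / 30% | 1.26 (265.9) | 1.02 | 1.00 | 35.9 |

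To set these shifts against chance in a single trial, use SE(log HR) ≈ 2/√events:
- 20%/10%: ln 0.916 = −0.088; SE = 2/√272.4 = 0.121; ratio −0.7.
- 30%/10%: ln 0.828 = −0.189; SE = 2/√266.6 = 0.122; ratio −1.5.
- 10%/30%: ln 1.257 = 0.229; SE = 2/√265.9 = 0.123; ratio 1.9.

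The 1.02 at equal shares is within simulation error: ln 1.016 = 0.016, against (2/√278.1)/√60 = 0.015.

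Two assumptions push these figures outward. In the column for the written rule, affected subjects become events only at death, although the rule would also count a further progression. And the assumed survival median of 72 months is twice the 3 years planned for placebo; earlier deaths would leave fewer next-line progressions to miss. The figures therefore show the direction and the possible order of size. They are not an estimate for this trial.

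**The case against.** **A first progression may be on record.** SAP 5.1 and the creatinine rows of Table 6 call for follow-up to PD, and Table 2 includes a response assessment at treatment discontinuation. Where a first progression was captured before next-line therapy, the written rule works. This stands as a limit: a reader might infer that the study never collects a first progression after a non-PD stop, and the documents do not support that. They conflict, because Protocol 8.1 and Table 2 provide no such assessment in survival follow-up.

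**The fallback already addresses it.** In the illustration it gave 0.98 to 1.02 throughout. That is real mitigation, but it rests on the assumed 3-month gap to the following therapy. The fallback is also conditional on OS and PFS2 not being reliably determinable, and it dates the event later than the next-line failure.

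**Bias is not shown.** No passage gives, by arm, the share reaching next-line therapy without documented PD, the number stopping for toxicity, or the number on treatment at either amendment. The amendments stop both arms, at different times. This objection stands in full.

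**The stakes are limited.** PFS2 is outside the fixed testing sequence in SAP 11, which lists only tumor response and duration of response, and OS is unaffected. That bears on priority, not on whether the rule is sound.

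**The timing is awkward.** The study is open-label from Amendment #10, so replacing a secondary definition now invites the charge of a data-driven choice. This is a good reason to keep the present analysis alongside the new one.

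**Conclusion.** The point holds on the plain wording of both documents: progression on next-line therapy with no earlier documented progression is not a PFS2 event at that time. The hazard ratio may be biased if the share of such subjects differs between arms; both direction and size are unknown. The illustrative range of about 0.83 to 1.26 under a true value of 1.0 depends on assumed unequal shares within 10% to 40% and on the assumed times above. With equal shares the value is about 1.0.

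Two stronger readings are tempting and not supported. One is that the PFS2 result is biased, in lenalidomide's favour, because toxicity stops fall mainly on that arm; the documents do not say so, and the Amendment #10 placebo stops could push the other way. The other is that these failures are lost. They are delayed, and may still count at a further progression, at death or, in the fallback, at the start of the following therapy. Subjects with progression documented before next-line therapy are unaffected.

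**What to change.** Before the PFS2 analysis, revise Protocol 16.3.2 and SAP 11.2.4 along these lines: *PFS2 is the time from randomization to the first objective progression after the start of next-line CLL therapy, or death from any cause, whether or not a progression was documented before that therapy. Subjects without such an event are censored at the last date known alive without it.*

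Report two sensitivity analyses routinely: the present second-progression count, and the fallback with start of the CLL therapy after next-line treatment as an event. Tabulate by arm the number starting next-line therapy without a documented progression, so that readers can see whether the shares differ.

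Reconcile the follow-up after non-PD stops between Protocol 8.1 and Table 2 on one side, and SAP 5.1 and Protocol Table 6 on the other. Correct the PFS label in Protocol 16.3.2.

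The cost is wording and a few extra outputs; next therapies and progression following next therapy are already collected. The downside is a small change to a secondary endpoint after unblinding. Keeping the present analysis makes the change transparent and retains second progressions that occur before any next-line therapy.

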### **16.3.3. Efficacy Analyses**

Kaplan-Meier product limit methods will be used to estimate the survivorship functions for the time-to-event endpoints (eg, OS, and PFS2). A two-sided log-rank test stratified by the 3 strata used in the randomization will be used as the primary analytic method to compare survivorship functions for time-to-event variables in the 2 treatment groups. In terms of the survivorship functions for each treatment group, the hypotheses of interest were:

$$H_0: F_A(t) = F_P(t) \text{ for all } t$$

Versus

$$H_1: F_P(t) \neq F_A(t) \text{ for all } t$$

where  $F_P$  is the survivorship function for placebo and  $F_A$  is the survivorship function for lenalidomide.

Median OS will be estimated using Kaplan-Meier estimates, and the 95% confidence intervals (CI) will be computed using the method of Brookmeyer and Crowley. Hazard ratio will be calculated using Cox model stratified for the 3 strata (ie, response to second-line induction chemotherapy, age, and presence of at least one prognostic factor) to account for the stratified randomization. The Cox model will also be used to identify prognostic factors.

Cross-tabulations will be provided by treatment group to summarize improvements from the best response during induction therapy.

## **16.4. Background and Demographic Characteristics**

Subjects' age, weight, height, and other continuous demographic and baseline variables will be summarized using descriptive statistics (mean, standard deviation, minimum, and maximum), while performance status, gender, race, and other categorical variables will be summarized with frequency tabulations for each treatment group separately and pooled over both treatment

regimens. Medical history data will be summarized using frequency tabulations for each treatment arm separately and pooled over both arms. Individual subject listings will be provided. Homogeneity of these variables will be assessed by one-way analysis of variance for continuous measures and Fisher's exact test for categorical measures.

### 16.5. Study Drug

Dosage statistics (mean, median, mode, standard deviation and final dose, dose at each evaluation) will be provided. Reasons for discontinuation will be summarized.

[REDACTED]

### 16.7. Safety Evaluation

All subjects who receive at least one dose of study medication will be included in the safety analyses.

Adverse events (AE) will be classified using the Medical Dictionary for Regulatory Activities (MedDRA) classification system. The severity of the toxicities will be graded according to the NCI CTCAE version 3.0 whenever possible.

The adverse event of infection will also be analyzed according to the grading system as recommended by the IWCLL guidelines for the diagnosis and treatment of CLL [REDACTED] ([Appendix 22.4](#)).

AE frequency will be tabulated by body system, MedDRA preferred term for each treatment regimen during the Treatment Phase. In the by-subject analysis, a subject having the same event more than once will be counted only once. AEs will be summarized by worst NCI CTCAE version 3.0 grade. AEs leading to death or to discontinuation from treatment, events classified as NCI CTCAE version 3.0 Grade 3 or higher, study-drug-related events, serious adverse events (SAEs), and events of interest (including second primary malignancies) will be summarized separately.

Laboratory data will be graded according to NCI CTCAE version 3.0 severity grade. Cross tabulations will be provided to summarize frequencies of abnormalities.

For vital sign and body weight data, means, medians, standard deviations, minimum, and maximum values will be provided.

Graphical displays will be provided where useful to assist in the interpretation of results.

